Each of the 12 subjects will participate in two blinded experimental sessions, assisted by either MDMA or placebo, of seven hours in duration within a brief course of non-drug therapy, including three hour-long preparatory sessions at the start of the study and three hour-long integrative sessions during the month after each experimental session at two week intervals. This study is designed as a dose escalation study to assist with the exploration of safety and finding the most effective dose in this population. Based on anecdotal reports, subjects in this population may be more sensitive to the standard dose of 125mg MDMA that has indications of efficacy for PTSD [68]. Subjects assigned to the MDMA group will receive two of three different doses, either 75mg, 100mg, or 125mg MDMA. Overall, eight subjects (66.7%) will be randomized to the MDMA group and four subjects (33.3%) will be randomized to the placebo group. During the study, there will be a maximum of 24 experimental sessions with MDMA, with eight sessions in each dose group, and eight experimental sessions with placebo. Observations before, during, and after experimental sessions will be compared between these groups of equal size to explore the effects of MDMA-assisted therapy in the first double-blind, randomized, placebo-controlled trial of this treatment for social anxiety in a sample of autistic adults.

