12.0 Data Analysis

This study is primarily a safety study that will also obtain estimates of effect size comparing MDMA vs. placebo using observer-blind data from the LSAS as the primary outcome measure. MDMA doses are not expected to differ greatly in treatment outcomes and will be combined for effect size estimates. Descriptive statistics will be computed overall for MDMA and placebo, and within the MDMA dose groups for all available data from outcome measures, including minimum, maximum, average, and standard deviation. Distributional characteristics will be examined for outliers and extreme values and, if either is evident, nonparametric statistics will be utilized in the analysis. Effect size for all outcome measures will be estimated using Cohen's techniques.

The sponsor will examine MDMA and placebo groups for homogeneity through comparing demographic characteristics. There is no expectation that conditions will differ in composition by gender, race or ethnicity, duration of autism diagnosis, or presence versus absence of other permitted psychiatric disorders, such as depression. However, owing to small sample size, such variations may arise by chance. If MDMA and placebo subjects differ upon a demographic variable, then the effects of this variable will be taken into account when looking at safety analyses. No systematic differences are expected.

Primary and secondary outcome measure scores will be plotted across each time of administrations for trend analyses. The number of intervals will vary in accordance with times listed for each measure, but will include in most cases baseline, one or more times after the first experimental session, one or more times after the second experimental session and at six month follow up. Plots will be made for MDMA and placebo subjects, and if trends occur for MDMA subjects, separate exploratory plots will be made for outcome measures after 0, 75, 100 and 125 mg MDMA.

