The main estimates of effect size from blinded data will be conducted after the outcome measure assessments at the six-month follow-up are complete for all subjects. Data from all doses of MDMA during Stage 1 (n=16), to be compared with all data from placebo sessions (n=8), with each experimental session treated as an independent observation. The MDMA condition will encompass both Group 1 and Group 2 MDMA doses. Estimates of effect size will be obtained from BDI-II, STAI, PSS, IRI, RSES, ERQ, TAS-20, and QoL-Q scores collected pre-treatment, during and after each experimental session, and the follow-up period, with p value set at 0.05. Effect size will be used to determine the appropriate sample size for future studies.

Scores for BDI-II, STAI, PSS, IRI and RSES completed after each of the experimental session will be averaged to produce mean scores for these periods, including a post-experimental session 1 and post-experimental session 2 average score. BDI-II, STAI and PSS scores gathered via postal mail at monthly intervals from two to five months after the second experimental session will be averaged to produce mean scores for the follow-up period. Missing responses will be replaced with the sample average. These averages will be used for estimates of effect size.

TASIT scores will be compared assessing baseline, after experimental session 1, after experimental session 2, at integrative session six and at 6-month follow up. Correlations between TASIT scores and LSAS scores at the time point following each TASIT score will be made to see whether increased awareness of social cues is associated with reduced social anxiety. MDMA dose will be used as a covariate in order to examine the potential relationship between dose and changes in one or more variable, with dose (75, 100 or 125 mg) serving as the covariate.

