Descriptive statistics will be computed for vital signs and subjective distress during each experimental or open-label session. The sponsor will compare pre-drug and post-drug peak blood pressure, heart rate, and body temperature during and after all experimental sessions by condition and MDMA dose. Analyses will compare peak vital signs between MDMA and placebo subjects, and a separate analysis will consider the effects of dose (0, 75, 100 or 125 mg MDMA) upon vital signs.

Frequency tables will be produced on prevalence of spontaneously reported reactions and AEs. Number and severity of spontaneously reported reactions will be compared in MDMA and placebo subjects using a one-way analysis of variance (ANOVA). The effects of MDMA dose upon number and severity of spontaneously reported reactions will also be assessed. Presence and degree of exacerbated symptoms across MDMA and placebo participant will also be examined.

Perceptions of study participation will be examined at baseline, 6-month follow-up, and end of Stage 2 using the Feedback Questionnaire and a qualitative interview. The results of this qualitative analysis will inform the sponsor of expectancies and perceptions about study procedures for future protocol development. Similarly, belief of condition assignments collected during Stage 1 will be used to assess the effectiveness of the double-blind in preparation for future studies. Results from the Feedback Questionnaire and safety data will be utilized to find the appropriate active MDMA dose for future studies.

To facilitate the planning of future studies, a preliminary estimate of effect size may be performed after all the subjects have completed the outcome assessments, one month after the second experimental session, but not all subjects have completed the six-month follow-up evaluation. This preliminary estimate will consist of safety and outcome measures. Results of the preliminary estimate will have no effect on study conduct.

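### Planned MDMA dose is tied to session number and enrolment Group, but the Protocol's dose comparisons account for neither, so a session or cohort shift would look like a gradient over 75/100/125 mg

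*Protocol*

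**What the plan says.** Protocol section 2.3 gives the escalation design the purpose "to assist with the exploration of safety and finding the most effective dose in this population". It foresees "a maximum of 24 experimental sessions with MDMA, with eight sessions in each dose group, and eight experimental sessions with placebo", and adds: "Observations before, during, and after experimental sessions will be compared between these groups of equal size".

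The dosing plan is in section 2.4 (Table 1), section 4.0 and section 6.2.1. Group 1 is the first six enrolled: 4 on MDMA at 75 then 100 mg, 2 on placebo. Group 2 is the second six: 4 on MDMA at 100 then 125 mg, 2 on placebo. Escalation depends on safety and tolerability. Placebo subjects may enter open-label Stage 2 at 75 then 125 mg (section 5.2.8).

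Section 12.0 plans these analyses by dose:

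- descriptive statistics "within the MDMA dose groups for all available data from outcome measures";
- if a trend is seen, "separate exploratory plots will be made for outcome measures after 0, 75, 100 and 125 mg MDMA";
- the dose covariate: "MDMA dose will be used as a covariate in order to examine the potential relationship between dose and changes in one or more variable";
- peak vital signs "during and after all experimental sessions by condition and MDMA dose", and then "a separate analysis will consider the effects of dose (0, 75, 100 or 125 mg MDMA) upon vital signs";
- an assessment of MDMA dose against the number and severity of spontaneously reported reactions, with no method given.

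None names session number or Group. Section 12.0 mentions the two Groups only to combine them as the MDMA condition. It also says that safety data and the Feedback Questionnaire will help to find the dose for future studies, and SAP section 2.0 says the data will inform future dosing. The SAP has no analysis by mg dose.

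**The concern.** No MDMA subject has a planned dose change that is not also a change from first to second session. Between subjects at the same session, a dose difference is always also a difference between the first and second six enrolled. Practice on the measures, accumulated therapy, familiarity with the drug, carry-over from session 1, or a change in who was recruited would each appear as a trend across 75, 100 and 125 mg.

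At stake is the reading of dose, which is a stated purpose of the trial. The pooled MDMA–placebo comparison is not touched, because both arms contribute equally from sessions 1 and 2.

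**Working it through.** **Session counts.** The plan's own totals reproduce: 8 MDMA subjects × 2 = 16 Stage 1 MDMA sessions, and 4 placebo subjects × 2 = 8 placebo sessions, as in section 12.0. If all four placebo subjects enter Stage 2, this adds 4 sessions at 75 mg and 4 at 125 mg, giving the 24 sessions, eight per dose, of section 2.3.

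| Dose | Stage 1 (session 1, session 2) | With Stage 2 (session 1, session 2) |
|---|---|---|
| 75 mg | 4, 0 | 8, 0 |
| 100 mg | 4, 4 | 4, 4 |
| 125 mg | 0, 4 | 0, 8 |

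Equal groups of eight therefore need sessions 1 and 2 pooled at 100 mg, and blinded Stage 1 pooled with open-label Stage 2 at 75 and 125 mg.

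**Identity.** Dose = 75 + 25 × (Group 2) + 25 × (session 2) gives 75, 100, 100 and 125 mg for the four Stage 1 cells, as planned.

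**Correlations.** Code dose as −1, 0, 1 and each factor as ±0.5.

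- Stage 1, session or Group: 4/√(8 × 4) = 0.71.
- All 24 MDMA sessions, session: 8/√(16 × 6) = 0.82.
- All 24 MDMA sessions, Group: 4/√(16 × 6) = 0.41.

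**False gradient with no dose effect.** The session-2 share is 0, 50 and 100% across the three doses, with or without Stage 2. A session shift D thus gives means 0, D/2, D. A Group shift G gives 0, G/2, G in Stage 1, and 0.25G, 0.5G, 0.75G with Stage 2 pooled. In Stage 1, equal and opposite shifts cancel.

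**Illustrative false-positive rates.** The documents give no D, G or within-subject correlation. I assumed shifts of 0.5 or 1 SD, correlation 0 to 0.5, total SD 1, two-sided 5% tests, and sessions analysed as independent. Section 12.0 states independence for the pooled comparison; extending it to the dose analyses is my assumption. Zero dose effect, simulated:

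| Analysis | No shift | 0.5 SD | 1 SD |
|---|---|---|---|
| 16 Stage 1 MDMA sessions, linear dose, session shift | 5.0–5.2% | 9.6–11.2% | 22–26% |
| Same, Group shift | 5.0–5.2% | 9.3–9.5% | 21–22% |
| Same sessions, three-level dose, session shift | 2.5–5.0% | 6–8% | 14–15% |
| Same, Group shift | 2.5–5.0% | 4–7% | 9–15% |
| 24 Stage 1 sessions, four levels (0/75/100/125 mg), session shift | 5–6% | 7–8% | 11–13% |
| Groups of eight, three active levels, session shift | 2.0–5.0% | 8–12% | 30–32% |
| Groups of eight, placebo as fourth level, session shift | 3.4–5.0% | 8–10% | 23–25% |

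A straight line from 0 to 125 mg through the 24 Stage 1 sessions gains no false positives from a session shift that is equal on placebo.

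**Can adjustment repair it?** In the Stage 1 MDMA subjects:

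- Intercept + linear dose + session + Group has rank 3 of 4. Subject terms + session + linear dose has rank 9 of 10. Neither identifies dose.
- Three-level dose + session fits the four cell means exactly. With a pure Group shift the cells (Group 1 sessions 1 and 2, then Group 2 sessions 1 and 2) are 0, 0, G, G. The 100 mg effect is G, the session effect is 0 − G = −G, and the 125 mg effect is G − (−G) = 2G. It removes D but doubles G.
- Taking the session effect from placebo requires it to be equal on MDMA. If the shift occurs on MDMA only, a model with fixed subject terms credits D to each 25 mg step, so 125 versus 75 mg is biased by 2D. Even when the assumption holds, a model with dose, session and Group raises the standard error of the slope per 25 mg from 0.354 to 0.612 SD (independent errors).

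**Same-session contrasts.** These are 75 versus 100 mg at session 1 and 100 versus 125 mg at session 2, each 4 versus 4. The 95% CI half-width is t(0.975, 6 df) × √(2/4) = 2.447 × 0.707 = 1.73 SD.

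**The case against.** The strongest reply is that little depends on these comparisons. They are exploratory, and section 12.0 expects doses to differ little and combines them for the effect sizes. The SAP compares treatment groups at Visit 13 (8.10.1, 8.10.2), tabulates reactions for each session (8.10.4), keeps data it does not analyse out of tables and graphs, and labels unplanned analyses as post hoc (8.0). The confounding comes from an openly stated escalation design.

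The error rates also belong to tests the documents do not specify. Descriptives and plots have no error rate, and no method is named for dose against vital signs or reactions. The four-level Stage 1 test, the plainest reading of the vital-signs analysis, inflates least of the session-shift cases at 1 SD, and by only about 2 points at 0.5 SD. The groups of eight rest on a purpose statement; nothing in section 12.0 expressly orders Stage 1 and Stage 2 pooled by dose.

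Most of this is fair and limits the weight of the point. It does not remove it. The SAP neither withdraws the Protocol's dose comparisons nor separates them by session. The outcome plots over time and the per-session vital-sign descriptives in section 12.0 are not tied to the dose analyses. A comparison over all three active doses has to pool sessions, because 75 and 125 mg never share one. The 0, D/2, D pattern needs no assumed test or shift size.

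**Conclusion.** The concern holds, as a matter to consider rather than a threat to the main result. If the dosing plan is followed, dose cannot be separated from session and Group in the MDMA subjects, and the planned dose comparisons do not acknowledge this. The identity is exact only as planned: a withheld escalation would alter it, and the Stage 2 counts assume that all four placebo subjects enter.

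The confounding is arithmetic; its practical size is unknown. Under the assumed shifts, a 1 SD session shift gives false-positive rates from about 11% to 32%, depending on the test and the sessions pooled, and a 0.5 SD shift gives about 6% to 12%. The dose analyses can describe what was seen at each dose in each session. They cannot support a dose-response reading across 75, 100 and 125 mg.

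**What to change.** In Protocol sections 2.3 and 12.0, and in the SAP if dose analyses will be run, add:

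> Outcomes, vital signs and reactions will be presented by dose and session number (100 mg shown separately for sessions 1 and 2), with Stage 2 shown separately. Dose is confounded with session number and with enrolment Group, so a pooled trend or comparison over 75/100/125 mg will not be read as dose response.

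The two same-session contrasts may be added as mean differences with 95% CIs, one observation per subject and no test. A note should say that they remove the session effect but are fully aliased with Group, use the same 4 versus 4 subjects twice, and carry different prior doses at session 2. If tested, a 1 SD cohort shift would make each falsely significant about 22% of the time and at least one 35–40% (9% and 16–18% at 0.5 SD), so they should stay descriptive. Any model with a session or subject term should be a sensitivity analysis with its assumption stated.

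The cost is wording and table layout; no dose or procedure changes. The trial gives up a formal dose-response claim from the pooled doses, and each Stage 1 dose-by-session cell holds only 4 MDMA subjects.

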 - To assess effects on self-esteem as measured by the Rosenberg Self-Esteem Scale (RSES) at baseline, within 24 hours after each experimental session, one month after each experimental session, and at the 6-month follow-up assessment.
 - To assess effects on state and trait anxiety as measured by the State-Trait Anxiety Index (STAI Form Y) at baseline, one day, two weeks, and one month after each experimental session, and monthly by mail leading up to the the 6-month follow-up assessment.

The following objectives will compare effects in specified subjects:

- To conduct a within-subject comparison of Stage 1 LSAS outcomes to Stage 2 open-label LSAS outcomes.
- To conduct a hierarchical regression analysis using condition assignment in Stage 1 and TAS-20 scores and OT, AVP, and CORT at baseline as predictors and LSAS outcomes as dependent variables.

The following objectives will include exploratory analyses intended to inform protocol design:

- To assess the ability of the investigators and subjects to accurately guess condition assignment in Stage 1.
- To assess perceptions about dose and study procedures at baseline and 6-month follow-up using a qualitative interview and feedback questionnaire.
- To determine feasibility of recruiting, testing and treating subjects on the autism spectrum with MDMA-assisted therapy as measured by enrollment rates, dropout rates, and completion of assessments and other study-related procedures.

3.3 Safety Objectives:

The safety of subjects will be assured during and after the experimental sessions by assessing physiological effects, psychological distress, AEs, spontaneously reported reactions and suicidality.

- Vital signs (BP, HR, temp.) will be measured at baseline and every hour during experimental sessions until they return to baseline.
- Participant distress will be measured by the Subjective Units of Distress (SUD) scale at baseline and every hour during experimental sessions until return to baseline.

- Risk of suicide will be measured by the Columbia Suicide Severity Rating Scale (CSSRS) during all in person visits, as well as twice during each experimental session at two hours after drug administration and the end of the experimental session, and on Day 2 and Day 7 after each experimental session.

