Biomarkers will be evaluated for predictive and prognostic power. Separate estimates of effect size will be performed for OT, AVP and CORT. Changes in biomarker concentrations from pre-treatment levels will be used to analyze effects of acute dosing and to determine the time-course of elevated OT and AVP levels post-drug. Pre-treatment biomarker concentrations will be evaluated for predictive power using an exploratory hierarchical regression analysis with condition assignment in Stage 1 and biomarker concentrations at baseline as predictors and treatment outcomes as dependent variables. One regression will be performed with biomarker values taken at the second experimental session. A second regression will be performed on biomarker values taken two weeks after the second experimental session.

TAS-20 scores will be evaluated for predictive power using an exploratory hierarchical regression analysis with condition assignment in Stage 1 and TAS-20 scores at baseline as predictors and with LSAS scores as dependent measures. One regression will examine the predictive power of condition and baseline TAS-20 scores upon LSAS scores one month after the first experimental session and the other will investigate whether condition and baseline TAS-20 and will predict LSAS score at one month after the second experimental session.

Subjects who discontinue treatment prior to the second experimental session will be asked to complete the final outcome assessment prior to continuing to the 6-month follow-up whenever possible. The data from these subjects will be tested for equivalence to data from subjects completing the study per protocol. If found to be equivalent, data from these subjects will be combined for an exploratory intent-to-treat effect size estimate to examine results without bias towards subjects more likely to complete the study per protocol.

Stage 1 and Stage 2 outcomes in extension subjects will be compared after the outcome measure assessments are complete for all extension subjects.

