- To explore whether TAS-20 scores and OT, AVP, and CORT levels at baseline predict LSAS scores at the primary endpoint

The following objectives will include exploratory analyses intended to inform protocol design:

- To assess the ability of the investigators and subjects to accurately guess condition assignment in Stage 1.
- To assess perceptions about dose and study procedures at baseline and 6-month follow-up using a qualitative interview and feedback questionnaire.
- To determine feasibility of recruiting, testing and treating subjects on the autism spectrum with MDMA-assisted therapy as measured by enrollment rates, dropout rates, and completion of assessments and other study-related procedures.

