Outcome measures will be assessed prior to treatment, during the treatment period, one month after each experimental session, and during the 6-month follow-up according to the Time and Events table. The sponsor will conduct an ongoing review of videos of therapy sessions, entry criteria, vital signs, and reaction data for completed sessions and any AEs. The sponsor will provide ongoing feedback to the co-therapist teams to ensure subject safety. Blood samples will be obtained for biomarker analysis at baseline and during the study according to the Time and Events Table. Biomarker analyses including plasma OT, AVP, and CORT will be explored as

surrogate endpoints at baseline, two hours after drug administration during the second experimental session, one month after the second experimental session, and at 6-month follow-up. Blood will be collected during the open-label extension Stage 2 two hours after drug administration during both experimental sessions and one month after both experimental sessions. Biomarkers will be evaluated for predictive and prognostic power. Subjects will complete a 6-month follow-up visit after completing Stage 1 or 2.

Table 1: Dose Regimen

Group # /Randomization /Sample	Stage 1		Stage 2 Open-Label	
	Session 1 Month 1	Session 2 Month 2	Session 1 Month 6	Session 2 Month 7
Group 1 Active (n=4)	75 mg	100 mg	N/A	N/A
Group 1 Placebo (n=2)	Placebo	Placebo	75 mg	125 mg
Group 2 Active (n=4)	100 mg	125 mg	N/A	N/A
Group 2 Placebo (n=2)	Placebo	Placebo	75 mg	125 mg

collected for seven days post experimental session; G = Independent Rater administered; H = May be recorded to video; I = Stage 2 subjects only; J = Only MDMA subjects will terminate.

Table 3: Time and Events Stage 2

Study Phase	Experimental Session	Integrative Sessions		Experimental Session	Integrative Sessions		
		V16	V17		V18	V19	V20
Visit #	V15	1 day later	2 Wks later	Apr. 1 Month after V15	1 day later	2 Wks later	2 Wks later
Visit Timing		✓ ^G	✓ ^G		✓ ^G	✓ ^G	✓ ^G
LSAS		✓ ^E	✓ ^G		✓ ^E	✓ ^G	✓ ^G
C-SSRS	✓ ^{A, C, D}	✓ ^E	✓ ^G	✓ ^{A, C, D}	✓ ^E	✓ ^G	✓ ^G
Feedback Questionnaire, Qualitative Interview							
Collect Concomitant Medication	✓	✓	✓	✓	✓	✓	✓
End Medication Taper (if applicable)	✓ ^I						
Collect Serology Samples (OT, AVP, CORT)	✓	✓	✓	✓	✓	✓	✓
Record to Video	✓	✓	✓	✓	✓	✓	✓
General Wellbeing	✓	✓	✓	✓	✓	✓	✓
Drug Screen	✓	✓	✓	✓	✓	✓	✓
Pregnancy Screen (if applicable)	✓	✓	✓	✓	✓	✓	✓
BDI-II, STAI		✓	✓		✓	✓	✓
PSS		✓	✓		✓	✓	✓
IRL RSES		✓	✓		✓	✓	✓
TASIT	✓			✓			

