8.10.3 Exploratory Analyses

Exploratory analyses of biomarkers will examine their ability to predict clinical outcome. Analyses will be performed for OT, AVP, CORT, and BDNF. Changes in biomarker concentrations from pre-treatment levels will be used to analyze effects of acute dosing and to determine the time-course of elevated biomarker levels post-drug. Pre-treatment biomarker concentrations will be evaluated in regression analysis with condition assignment in Stage 1 and biomarker concentrations at baseline as predictors and treatment outcomes as dependent variables. Additionally, the effect of biomarker levels taken at the second experimental session, and two weeks and six months after the second experimental session, will be examined for correlation with LSAS outcomes.

Distributional characteristics will be examined for outliers and extreme values. If outliers are found in primary or secondary outcome measures, the sponsor will perform analyses with and without the outlying data.

Post-hoc exploratory analyses not identified in this SAP may be performed to further examine the study data. These analyses will be clearly identified as such in the final clinical study report.

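### The exploratory TAS-20 and biomarker regressions leave out baseline LSAS, so severity at entry can pass as prediction; for the biomarkers, the named terms can show prognostic association only.

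*Protocol*

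**What the plan says.** **TAS-20.** Protocol 12.0 describes a hierarchical regression with "condition assignment in Stage 1 and TAS-20 scores at baseline as predictors and with LSAS scores as dependent measures". Two fits are planned. The first examines "the predictive power of condition and baseline TAS-20 scores upon LSAS scores one month after the first experimental session"; the second asks whether the same two terms "will predict LSAS score at one month after the second experimental session". The outcome is thus the follow-up score, not change. In the SAP, TAS-20 prediction appears only as an objective in 3.2: "To explore whether TAS-20 scores and OT, AVP, and CORT levels at baseline predict LSAS scores at the primary endpoint". SAP 8.10.3 contains no TAS-20 regression.

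**Biomarkers.** Protocol 3.2 lists a regression with "condition assignment in Stage 1 and TAS-20 scores and OT, AVP, and CORT at baseline as predictors and LSAS outcomes as dependent variables". SAP 8.10.3 specifies "condition assignment in Stage 1 and biomarker concentrations at baseline as predictors and treatment outcomes as dependent variables". The aim is given in SAP 4.0, and in the same terms in protocol 4.0 and 12.0: "Biomarkers will be evaluated for predictive and prognostic power".

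**What is absent.** Neither document puts baseline LSAS or a condition-by-predictor term in any of these models. The protocol calls them hierarchical without listing the blocks, and the SAP drops the word. By contrast, the primary analysis in SAP 8.10.1 is on change from baseline, and protocol 5.2.1 has the blinded rater administer the LSAS at screening. The missing covariate is already in the data.

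**The concern.** Two separate weaknesses arise.

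1. **Baseline severity.** A subject who enters with high social anxiety will tend to score high later. If alexithymia or a hormone level goes with social anxiety at entry, it will be associated with the later score for that reason alone. A model without baseline LSAS cannot tell this from a predictor that adds information about outcome.

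2. **Predictive versus prognostic, for the biomarkers.** A prognostic marker is related to outcome whatever the treatment. A predictive marker, in the sense that contrasts with prognostic, is one whose relation to outcome differs between arms. A model with condition and marker as its only terms fits one slope for both arms, so it has no quantity that measures the second property.

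The study is meant to inform the design of later ones. A measure that only reflects entry severity could be reported as a marker of outcome, or a prognostic association as a marker of response to MDMA. SAP 2.0 applies no multiplicity correction, so nothing later in the plan limits this.

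**Working it through.** The documents give no error rate, power or effect size for these regressions, so there is no figure of theirs to reproduce.

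**Inputs from the documents.** 12 subjects, 8 MDMA and 4 placebo (protocol 5.3); two-sided tests (SAP 8.0). The 0.05 level is stated for other analyses (protocol 12.0, SAP 8.10.1) and is assumed to apply here.

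**Assumptions not in the documents.** Scores are standardised to SD 1. The correlation of predictor with baseline LSAS is r1, and that of baseline LSAS with Visit 13 LSAS (a month after session 2) is r2. The arm effect is 1 SD. Visit 13 LSAS depends on baseline LSAS and arm only, so the null is no association between predictor and Visit 13 LSAS given baseline LSAS.

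**Models and residual df**

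- Planned: LSAS on condition + predictor, 12 − 3 = 9.
- Adjusted: planned + baseline LSAS, 12 − 4 = 8.
- With interaction: adjusted + condition × predictor, 12 − 5 = 7.

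**Share of simulated trials in which the predictor is significant**

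| r1 / r2 | Planned | Baseline LSAS added |
|---|---|---|
| 0 / 0.7 | 5% | 5% |
| 0.3 / 0.6 | 8% | 5% |
| 0.5 / 0.6 | 14% | 5% |
| 0.5 / 0.8 | 24% | 5% |
| 0.7 / 0.8 | 45% | 5% |

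The four correlated rows come from 6,000 trials each; larger re-runs agree within about two percentage points. A wider grid (r1 from 0 to 0.7, r2 from 0.5 to 0.9, arm effect 0.8 SD) gives 5% to 59% for the planned model and about 5% with baseline LSAS.

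**Hand check of the last row.** Within arm, the predictor correlates with Visit 13 LSAS at r1 × r2 = 0.7 × 0.8 = 0.56. With 7 + 3 = 10 within-arm degrees of freedom for the predictor, the expected t is about 0.56 × √10 / √(1 − 0.56²) = 1.77 / 0.83 = 2.1. The critical value on 9 df is 2.26, so a rate a little under one half is right.

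**Change as the outcome.** In this set-up the correlation of predictor with change is −r1 × √((1 − r2)/2): −0.13, −0.22, −0.16 and −0.22 in the four correlated rows. It is not zero, because subjects who start high fall back more. Regressing change on condition + predictor flags the predictor in 7–10% of trials, so change scores cure the problem only in part.

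**One common slope.** The next three cases have a predictor independent of baseline LSAS, r2 = 0.7 and arm effect 0.8 SD. The planned model flags:

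- a purely prognostic marker (slope 0.7 in both arms) in 49% of trials;
- a marker acting only under MDMA (slopes 0 and 0.7) in 27%;
- a marker with opposite slopes (−0.67 on placebo, −0.67 + 1.0 = 0.33 on MDMA) in 6.5%.

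The third case was chosen so that the slopes nearly cancel: (7 × 0.33 − 3 × 0.67)/10 = 0.03. A significant result does not separate the first case from the second, and a null result does not exclude the third.

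**What an interaction term would deliver.** On 7 df, with r1 = 0.5 and r2 = 0.7, its power is about 12%, 32% and 55% for slope differences of 0.5, 1.0 and 1.5 SD of LSAS per SD of predictor. Roughly, the standard error is √(1 − 0.7²) × √(1/7 + 1/3) = 0.71 × 0.69 = 0.49. The 95% interval is then about ± 2.36 × 0.49 = ± 1.2, or wider.

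**The case against.** The strongest reply is that the models answer the question the plan asks. SAP 3.2 asks whether baseline values predict the LSAS score, and in the simulation they do, with within-arm correlations r1 × r2 from 0.18 to 0.56. A rejection detects a real association, so the 8–45% are errors only for the narrower question of information beyond baseline severity. This stands as a limit on how the percentages may be described. It does not remove the problem, because an association explained wholly by entry severity says nothing new about the predictor.

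Other points that stand:

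- All the correlations are assumed. At zero correlation there is no inflation, and the documents make no case that any hormone is correlated with LSAS.
- For the biomarkers the outcome term is general. It could mean change scores, though protocol 3.2 and SAP 3.2 point to LSAS outcomes or scores.
- The word hierarchical leaves room for further blocks, but none is specified.
- An interaction estimated with four placebo subjects is of little inferential use, so it is a debatable remedy.

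A reader might go further and infer that the plan cannot test the predictive power of TAS-20 either. The documents do not support that. Protocol 12.0 attributes predictive power to condition as well as to TAS-20, so there the phrase means explaining the outcome, which a main-effects model can do. Only for the biomarkers is predictive set beside prognostic.

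A reader might also take the inflation to affect an interaction test. It does not: in the same scenarios a condition-by-predictor term fitted without baseline LSAS was significant in about 4–5% of trials.

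**Conclusion.** The point holds in limited form. The TAS-20 regression explicitly uses follow-up LSAS without baseline LSAS, and the biomarker regressions name no baseline LSAS either. A predictor that adds nothing beyond baseline LSAS would be significant in about 8% to 45% of trials over the four correlated scenarios, and in 5% if it is unrelated to entry severity. Adding baseline LSAS brings this to about 5% in each. The size rests wholly on assumed correlations, so the supportable statement is that severity can pass as prediction, not that it will.

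For the biomarkers only, the terms named can show prognostic association and cannot address the predictive half of the stated aim.

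It would be wrong to infer that the efficacy result is at risk. These are exploratory analyses, no rule in the plan carries a marker forward, and the primary comparison on change in LSAS does not use these models. Baseline adjustment is the part that matters most.

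**What to change.** In protocol 12.0 and SAP 8.10.3:

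1. Fit one predictor at a time: LSAS at the stated visit on baseline LSAS + condition + predictor. Describe the predictor's coefficient as prognostic and report it with its confidence interval.
2. Name the outcome of the biomarker models explicitly, and add the TAS-20 model to SAP 8.10.3, where it is missing. If hierarchical is kept, list the blocks and their order.
3. For the biomarkers, either reword the aim as prognostic only, or add a condition-by-biomarker term and report its estimate and confidence interval as descriptive, with no claim based on its significance.

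The cost is a change of wording and one residual degree of freedom (9 to 8), or two (9 to 7) where the interaction is added. No new data, visit or procedure is needed. The drawback of the interaction is its imprecision with four placebo subjects, which makes rewording the aim the cheaper choice.
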